
Missing data

Missing data will be handled as required by the statistical methods used:

1. For most analyses this means excluding the observations for which a relevant value is missing.
2. For some analyses, such as decision trees, missing values will be grouped together to create a new category.

Outliers

Outliers will be handled using a method appropriate for the statistical method used. For example, they may be excluded for parametric methods, however, they may be included when using non-parametric methods. If a non-parametric method cannot be used (e.g., none exist or they are not sufficiently interpretable), then the outlier may be excluded or replaced with a more appropriate value (e.g., a randomly selected value, the median, or one determined via an imputation method such as Multiple Imputation by Chained Equations). Results with and without the outlier will be compared to determine whether its exclusion impacts conclusions.

Sub-group analyses

Sub-group analyses will be performed for variables for which there is existing evidence (e.g., in the literature) or reason to suspect that they differ between groups. Such analyses may be performed as separate analyses (e.g., one analyses per group) or via incorporation of the grouping variable into the statistical model as in linear or logistic regression.

Handling confounding variables

When possible, confounding variables will be incorporated into models to control for their effects, e.g., in logistic regression. Whether confounders are included exclusively as direct effects or as direct effects plus interaction terms depends on the clinical nature of the variable. The most appropriate method of inclusion will be determined via discussions between medical staff and a statistician and/or bioinformatics analyst.

11.2 Sample Size:

Assuming attrition and accounting for screen failures, we are requesting to enroll up to 200 (50 per arm) participants in order to evaluate a final sample of 92 (30-31 per arm).

11.3 Total number of subjects requested (including records and specimens):

200

11.4 If you are recruiting by study arm, please identify the arms of the study and how many subjects will be enrolled in each arm

Up to 200 participants will be randomized 1:1:1:1 to the four treatment arms.

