11.5 Please provide a justification for your sample size

Since this is a discovery-based study of a novel topic, limited data are available with which to perform a power analysis. Thus we used a G*Power for a general comparison analysis without needing to root firmly in one specific variable.

If we are able to enroll 150 participants (a minimum of 92 post-attrition), assuming an effect size of .2, we will achieve 90% power. Effect size assumptions were taken from Tomazoni et al. 2016 based on the comparison of control versus PBMT with regards to biomarkers of gene expression that we assume to be an acceptable proxy for our primary comparison with regards to our biomarkers of concern. Significance threshold for power calculations was considered to be .01 to account for false discovery rate within our set of primary biomarker outcomes. Power calculations were performed using the WebPower package and the R Programming language.

11.6 Data Analysis Plan: Complete description: Background, Objectives, Design, Step by Step how the project is going to be done, Data analysis plan:

Aim 1 will be evaluated by comparing the PRP only and the PRP + PBMT treatment arms at six weeks relative to baseline. Generalized additive models predicting the fractional change in outcome measure at 6 weeks will be used.

Aim 2 will compare across all four treatment arms and will use Multi-Level models comparing the three treatment arms across time points and including random effects.

Aim 1 will include biomarker measures only; Secondary Aim 2 will include both biomarker measures and self-reports.

Hypothesis tests will be two-tailed and statistical significance will be considered at the putative threshold ($\alpha=0.05$). Any secondary P-values will be subject to a false discovery rate adjustment in keeping with best statistical practices. Multilevel models will incorporate random effects to account for repeated measures, using distribution families and link functions appropriate for the outcomes of interest, determined using QQ plots analyzed for best model fit. All statistical analyses will be performed using the R Programming language.

Clinical outcomes (pain scores) will be evaluated via ANOVA and post-hoc tests (Tukey's HSD test). A non-parametric alternative will be used if assumptions are not met.

Molecular Analyses:

DNA/RNA Analyses

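### The subgroup plan permits separate per-group analyses and does not require a treatment-by-subgroup interaction, so it need not test whether the treatment effect differs

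*Combined protocol and SAP*

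**What the plan says.** Section 11.1, under the sub-group heading, sets an open rule for choosing variables: "Sub-group analyses will be performed for variables for which there is existing evidence (e.g., in the literature) or reason to suspect that they differ". It names no variable and gives no number of them. On method it says: "Such analyses may be performed as separate analyses (e.g., one analyses per group) or via incorporation of the grouping variable into the statistical model", with linear and logistic regression as examples. It gives no rule for choosing between the two routes.

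Interaction terms are mentioned in the next paragraph of 11.1, which concerns confounders, and they are optional there: "Whether confounders are included exclusively as direct effects or as direct effects plus interaction terms depends on the clinical nature of the variable".

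Section 11.6 supplies the testing rules. "Hypothesis tests will be two-tailed", at a threshold of 0.05, and "Any secondary P-values will be subject to a false discovery rate adjustment in keeping with best statistical practices". It does not say whether subgroup P-values belong to that adjusted set. The sample-size justification in 11.5 uses a stricter level: "Significance threshold for power calculations was considered to be .01 to account for false discovery rate".

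**The concern.** A claim that treatment works better in one group than another is a claim about the difference between two effects. A P-value from each group tested alone says only whether each effect differs from zero. When the true effect is the same in both, chance alone will often put one P-value below the threshold and leave the other above it.

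Putting the grouping variable into a regression helps only if its product with treatment is also included. As a main effect it adjusts for group but still assumes one common treatment effect.

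At stake is the reading of the results. Section 9.5 aims to generalise to service members and civilians, so statements about who benefits are foreseeable. An analyst could follow the sub-group paragraph to the letter and never compare the effects.

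**Working it through.** **Inputs from the plan.** Two-sided tests at 0.05 (11.6); planning alpha 0.01, effect size .2 and 90% power (11.5); 92 evaluable, described as 30-31 per arm, and up to 50 enrolled per arm (11.2); four arms allocated equally (11.4). Ninety-two over four arms is 23 per arm, whereas 30-31 per arm fits three arms (92/3 = 30.7). Both are therefore used, with 50 as the upper bound.

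**Assumptions, because the plan gives no figures.** One two-level subgroup split 50:50, a two-arm contrast, a standardised outcome, and the same true effect d in both halves.

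**The plan's own power figure.** Section 11.5 says "assuming an effect size of .2, we will achieve 90% power" without naming the metric. Read as f² with three groups (2 numerator degrees of freedom), N = 92 and alpha 0.01, the noncentrality is 0.2 × 92 = 18.4 and the noncentral F gives 0.901, which reproduces the 90%. With four groups the same reading gives 0.854. For two groups, f² = 0.2 corresponds to d = 2√0.2 = 0.89. The range of d used here therefore runs from 0.2 (the figure read as d) to 0.89 (the figure read as f²).

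**Separate tests.** With n per arm, each half has n/2 per arm. Its power p comes from the noncentral t with n − 2 degrees of freedom and noncentrality d√(n/4). The halves are independent, so P(exactly one significant) = 2p(1 − p).

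Example: n = 23, d = 0.5, alpha 0.05 gives p = 0.208, and 2 × 0.208 × 0.792 = 0.33.

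| Alpha | n per arm | d = 0.2 | d = 0.5 | d = 0.89 |
|---|---|---|---|---|
| 0.05 | 23 | 13.8% | 33.0% | 49.8% |
| 0.05 | 31 | 15.4% | 39.4% | 44.0% |
| 0.05 | 50 | 19.0% | 48.4% | 22.2% |
| 0.01 | 23 | 3.5% | 13.2% | 39.9% |
| 0.01 | 31 | 4.1% | 18.6% | 48.4% |
| 0.01 | 50 | 5.8% | 31.1% | 43.3% |

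The quantity 2p(1 − p) cannot exceed 50%, which it reaches at p = 0.5. It therefore rises and then falls with d, and values between the columns can exceed those shown, up to that ceiling.

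**Same result by overall power (normal approximation, alpha 0.05).** With z = 1.96 + z(power), each half has p = P(Z > 1.96 − z/√2). Overall power of 50%, 80% and 90% gives p = 0.283, 0.508 and 0.630, and so 41%, 50% and 47%.

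**Interaction test.** With equal effects it rejects at its nominal level, 5% or 1%. Simulation (20,000 runs) gave 5.1% at the 5% level, and only 10-12% of the one-group-only results also had a significant interaction.

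**Power of the interaction.** With a 50:50 split, its standard error is twice that of the overall contrast. If the overall contrast has 90% power, its expected z is 1.96 + 1.28 = 3.24. An interaction of the same size has expected z of 1.62, and power Φ(1.62 − 1.96) = 0.37.

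**The case against.** *The model route already allows an interaction.* It does. Nothing in the sub-group paragraph excludes one, 11.1 also provides for multi-way ANOVA, and the confounder paragraph contemplates interaction terms. A reader might infer that neither permitted route can give a valid subgroup comparison. The documents do not support that: the model route can, if a treatment-by-group term is added. What stands is that the term is not required and the other route cannot supply the comparison.

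*No subgroup claim is planned.* Aims 1 to 4 contain no subgroup hypothesis and the study calls itself discovery-based. A reader might infer that the plan commits to claims that treatment works in one group only. It does not; the harm is a risk of interpretation. That limits the seriousness but does not make separate tests answer the question.

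*The false discovery rate rule covers it.* If subgroup P-values fall under it, the rates above would change. But it adjusts for the number of P-values and does not compare effects between subgroups.

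*The rates depend on assumptions.* They do. Figures near 50% need fairly high overall power: at 23 per arm and alpha 0.05, d = 0.2 gives only 10% overall power and a rate of 14%. At d = 0.2 and alpha 0.01 the rate is about 4-6%. Twenty-three per arm is itself derived, since 11.2 prints 30-31.

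**Conclusion.** The point holds as a gap in the wording: the plan permits separate subgroup tests and nowhere requires the interaction that would compare effects. With equal true effects in two equal halves, the separate-test route shows significance in exactly one half in about 14% to 50% of trials at 23 per arm and alpha 0.05. The figures are 15% to 44% at 31 per arm and about 3.5% to 48% at alpha 0.01 for 23 to 50 per arm, all at the tabulated effects and before any false discovery rate adjustment. The interaction test errs in 5% (or 1%). These sizes rest on assumed effects of 0.2 to 0.89 and one 50:50 split. It is a minor improvement and does not undermine the main analyses.

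**What to change.** Replace the sentence on method in the sub-group paragraph of 11.1 with:

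> Whether a treatment effect differs between subgroups will be judged by the treatment × subgroup interaction in the model used for that aim (estimate and confidence interval), with the interaction P-values included in the false discovery rate family; within-subgroup estimates and confidence intervals are descriptive only.

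The wording refers to the model for each aim because 11.6 uses generalized additive models for Aim 1, multilevel models for Aim 2 and ANOVA for pain scores.

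It would help to list the subgroup variables as well, so that the size of the adjusted family is known. Five independent interaction tests at 0.05 without adjustment would give at least one false positive with probability 1 − 0.95⁵ = 22.6%.

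The cost is wording only, with no change to design, data or sample size. The downside is low interaction power (about 37% in the case shown above), so fewer subgroup claims will be made. The plan should say so, and should add that a non-significant interaction does not show that effects are equal.

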10.0 Study Procedures, Data Management, and Privacy

10.1 Study Procedures:

Describe step-by-step how the study will be conducted from beginning to end

Recruitment, Pre-Screening (before consent), Study Introduction & Informed Consent:

About 1927 dependents and 1416 retirees with knee OA cases are seen by Madigan's Orthopaedic's department every year; 77 cases of knee pain and 135 patellofemoral OA were seen in the active-duty population. Thus, we should be able to recruit 150 participants in the next 2 years.

Potential participants will be identified via four methods:

1. Under the provisions of an approved Partial HIPAA Waiver Application for this study, local study team members will review medical records of patients coming in to the Sports Medicine, Physical Therapy, Orthopedic, Podiatry, and Physical Medicine & Rehabilitation (PM&R) clinics for suspected/confirmed knee OA in order to identify prospective research participants and to seek their authorization to participate/use their protected health information for this research study. The study team will receive approval from the potential participant's provider prior to approaching for possible study participation. As indicated in the Partial HIPAA Waiver Application for this study, the minimal amount of PHI necessary to screen for participants includes:
 - Names
 - Dates (except year) directly related to an individual (such as birth date, date of clinic visits, etc.)
 - DoD ID number
 - Relevant medical history (current and/or previous diagnoses and/or symptoms reported for the knee and associated treatments)
2. Direct referral from local healthcare providers in the local Sports Medicine, Family Medicine, Orthopedic and Podiatry, Physical Therapy, Holistic Health and Fitness (H2F), and Physical Medicine & Rehabilitation (PM&R) clinics.
3. Patients may self-refer to participate in the study. Interested potential participants will be able to contact a member of the study team via phone or email. Potential participants who contact the study team directly will be instructed to seek care with Orthopaedics, Sports Medicine, PM&R, or their primary care manager for a physical exam for a diagnosis of knee OA, if they do not already have a diagnosis.
4. Study advertisements will be posted within the following locations, and copies will be provided to clinic staff:
 - Internal Medicine
 - Aviation Medicine
 - H2F
 - McChord Clinic
 - Winder Clinic
 - Okubo Soldier-Centered Medical Home

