As part of the formal screening procedures, all consented participants that are biological females of child-bearing age and capacity will be required to complete a urine hCG pregnancy test, which will be ordered via EMR by a study provider, to confirm eligibility for study participation. MAMC Department of Pathology and Area Laboratory Services (DPALS) will complete urine sample collection and analysis and upload results in the participant's EMR. If the pregnancy test is positive, per the inclusion/exclusion criteria, the participant will be formally withdrawn from the study at this point, and will be encouraged to seek care with their primary care physician. If the pregnancy test is negative, the participant will be eligible to continue with the study procedures. The results of the pregnancy test will be entered into the EMR.

As part of the formal screening procedures, consented participants' final eligibility status will be confirmed via weightbearing knee X-rays, including AP, Rosenberg (45 deg knee flexion with beam from Posterior to anterior), and lateral views. If imaging was completed within one month prior to study enrollment, the previous images may be utilized. If diagnostic images are required, imaging will be ordered by an authorized medical provider. The results of the diagnostic images will determine if the participant meets final eligibility criteria (Kellgren-Lawrence grade 2 or higher, which demonstrates possible narrowing of the joint space with definite osteophyte formation), and should continue with the study intervention. A study physician will order X-Rays,

including AP, Rosenberg (45 deg knee flexion with beam from Posterior to anterior), and lateral views, or knee OA diagnosis. We will remove all personal identifying information from the images and only associate the images with the participant's assigned participant ID. These images will be stored securing within the TeleRay data platform. Please see Sections 10.14-10.15 for more information regarding Teleray.

Formal screening and confirmation of final eligibility status will be completed prior to study randomization.

Demographics & Baseline Data Collection:

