Synovial fluid will be aspirated according to standard of care (SOC) guidelines. If, at the time of joint aspiration, there is a "dry tap" (i.e., no fluid is returned), the provider will lavage the joint with a standardized quantity (10ml) of sterile Normal Saline and then aspirate the lavage. There are no harmful effects from lavaging the synovial joint with sterile saline.

The synovial fluid will be labeled with a sample ID and study visit, and transported to MAMC Department of Clinic Investigation (DCI) for storage and processing. Any excess synovial fluid will be safely discarded per standard protocol. Ice will be utilized when necessary.

Synovial fluid processing and storage are outlined below in respective sections.

The research team will maintain a biospecimen sample master key that links the sample IDs to the participant study IDs. No PII/PHI will be stored with the biospecimen sample key.

Randomization:

Participants that meet final eligibility criteria will be randomized to a study arm using a computer-generated randomization model prepared by the study biostatistician, to assign participant 1:1:1:1 across all study arms (PT, PT+PRP, PT+PBMT, or PT+PRP+PBMT).

Study Intervention:

Study interventions will be documented in the participant's EMR and on the Study Treatment Documentation Log (Appendix F).

Standard of Care (SOC) Physical Therapy (PT):

All participants will complete a standard PT program addressing individual strength, mobility, and flexibility deficits in both proximal and distal muscle groups. The provider may also use other modalities to address distal issues. If a participant has not been placed on profile at the time of consent, a profile may be written by the study medical provider to ensure limitation of activities, as appropriate.

The PT treatment participants receive in this study will be standard of care; that is, the PT treatment regimen will not be standardized across study participants and/or dictated by study-specific criteria. PT treatments will be recorded on a Chart Review CRF (Appendix I).

SOC PT + Platelet-Rich Plasma (PRP):

In addition to SOC PT, participants assigned to PT+PRP group will receive PRP treatment, as outlined below.

PRP Preparation:

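### The final sample of 92 does not match 30-31 per arm in a four-arm trial, and the 90% power attached to 92 is not shown to hold for that design

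*Combined protocol and SAP*

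**What the plan says.** All places are in the combined protocol and SAP.

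- **Allocation.** Section 10.1 (Randomization) uses a computer-generated list "to assign participant 1:1:1:1 across all study arms (PT, PT+PRP, PT+PBMT, or PT+PRP+PBMT"). Section 11.4 agrees: "Up to 200 participants will be randomized 1:1:1:1 to the four treatment arms".
- **Target sample.** Section 11.2 sets the ceiling: "Assuming attrition and accounting for screen failures, we are requesting to enroll up to 200 (50 per arm) participants". The same sentence then gives the evaluable target that this ceiling is meant to deliver: "in order to evaluate a final sample of 92 (30-31 per arm").
- **Power.** Section 11.5: "If we are able to enroll 150 participants (a minimum of 92 post-attrition), assuming an effect size of .2, we will achieve 90% power". The threshold for that calculation is .01, chosen to allow for false discovery among the primary biomarkers. The effect size comes from a control-versus-PBMT comparison in a cited study, "that we assume to be an acceptable proxy for our primary comparison with regards to our biomarkers of concern". The section names both G*Power and WebPower, but no test, effect metric or number of groups.
- **Analysis.** Section 11.6 sets two-tailed tests at .05 and promises false-discovery-rate adjustment for secondary P-values. Aim 1 compares PRP with PRP + PBMT on biomarkers. Aim 2 is labelled secondary, and its sentence mentions both four and three treatment arms.
- **Arms elsewhere.** The end of section 9.2 and Aims 2-4 in 9.3 list three treatments. Section 9.4 and the primary objective in the IRB approval memorandum list four.
- **Recruitment.** Section 10.1: "Thus, we should be able to recruit 150 participants in the next 2 years".

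**The concern.** Section 11.2 uses two arm counts in one sentence: 200 is divided by four to give 50, while 92 yields 30-31 only if divided by three. The final sample and the per-arm number cannot both be right for the trial being run.

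Two things depend on this. First, section 11.1 drops participants with missing baseline or 6-week data from the Aim 1 analyses, so the evaluable number per arm sets the precision of that comparison, and the study team has no clear retention target. Second, the 90% power is tied to the total of 92. If 92 is the true total, each arm is a quarter smaller than the per-arm figure suggests (23 against 30.7), and nothing in section 11.5 shows that the power refers to four arms. The alpha used for power also has no counterpart in the stated rule for the primary tests.

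**Working it through.** **Step 1. Sample arithmetic** (inputs from 10.1, 11.2, 11.4 and 11.5)

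- 200 / 4 = 50, as section 11.2 states.
- 92 / 4 = 23 per arm; 92 / 3 = 30.7 per arm.
- 4 x 30 = 120 and 4 x 31 = 124.
- Retention implied by 11.5: 92 / 150 = 61.3%, that is 38.7% lost.
- The same retention applied to the ceiling in 11.2: 200 x 92 / 150 = 122.7, and 122.7 / 4 = 30.7 per arm.

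So 30-31 per arm has two possible origins: a three-arm total of 92, or a four-arm total of about 123 from 200 enrolled. The documents do not choose between them.

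**Step 2. Reproducing the 90%** (N = 92, effect size .2, alpha .01, from 11.5)

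Assumption: .2 is f-squared in a one-way F test. The noncentrality is lambda = f-squared x N, with k - 1 and N - k degrees of freedom, and power is the probability that the noncentral F exceeds the central critical value.

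- 2 numerator df (three groups), N = 92: lambda = 0.2 x 92 = 18.4, power 90.1%. At N = 91 it is 89.7%, so 92 is the smallest N that reaches 90%.

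**Step 3. The same model with four groups** (3 numerator df)

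| N | lambda | Power, alpha .01 |
|---|---|---|
| 92 | 18.4 | 85.4% |
| 102 | 20.4 | 89.99% |
| 103 | 20.6 | 90.4% |
| 120 | 24.0 | 95.2% |
| 124 | 24.8 | 95.9% |

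At alpha .05, N = 92 gives 95.5%.

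**Step 4. Other readings of .2** (four groups, N = 92, alpha .01)

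- .2 as f in a one-way test (f-squared = .04): 13.4%.
- .2 as f in a group-by-time test with m times and correlation rho, where lambda = f-squared x N x m / (1 - rho) and the degrees of freedom are 3(m - 1) and 88(m - 1):
  - two times: 74% at rho = .5 and 91% at rho = .65;
  - three times: 86% at rho = .5 and 90% at rho = .55.

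The documents give no correlation, so these rho values are assumptions. Across the readings shown, power at N = 92 runs from 13% to 91%.

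**Step 5. What the per-arm number changes, whatever .2 means**

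Difference detectable at 90% power in a simple two-sided comparison of two means, with noncentrality d x sqrt(n / 2):

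| Evaluable per arm | alpha .05 | alpha .01 |
|---|---|---|
| 23 | 0.98 SD | 1.18 SD |
| 30 | 0.85 SD | 1.03 SD |
| 31 | 0.84 SD | 1.01 SD |

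Aim 1 is to be analysed with generalized additive models on fractional change, so these values are a guide to scale only.

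**Step 6. Alpha**

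Section 11.5 powers at .01 because there are several primary biomarkers. Section 11.6 tests at .05 and limits its false-discovery commitment to secondary P-values. No sentence carries the .01, or an equivalent adjustment, into the primary tests.

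**The case against.** The strongest defence is that 30-31 per arm is the intended figure and only the total is stale. The retention in 11.5 applied to 200 gives 30.7 per arm over four arms, and on the f-squared reading 120-124 evaluable would exceed 90% power. This is plausible, but it is an inference: 11.5 still gives 92 as the minimum and attaches the 90% to it. The contradiction in the text remains.

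Four stronger readings are tempting and are not supported.

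- **That the power calculation was carried over from a three-arm trial.** The match at 92 needs only 2 numerator degrees of freedom. A regression with two predictors, or a four-arm model with PRP and PBMT as two main effects, would give the same 90.1%. The documents state none of these models, so the origin is unknown.
- **That Aim 1 is the powered comparison and is underpowered.** The secondary label on Aim 2 in 11.6 points towards Aim 1, but the IRB memorandum gives the comparison of all four treatments as the primary objective, and the effect size comes from control versus PBMT, which is not the Aim 1 contrast. No power figure for Aim 1 can be held against the plan.
- **That 200 and 150 contradict each other.** The first is a ceiling and the second a condition and a feasibility estimate. A real ambiguity remains: 11.2 counts screen failures within the 200 and gives 50 per arm, while 10.1 says "Formal screening and confirmation of final eligibility status will be completed prior to study randomization", so it is unclear whether 200 counts consented or randomised participants.
- **That the alpha mismatch inflates the power claim.** Powering at .01 and testing at .05 is conservative for power (85.4% becomes 95.5% in the four-group f-squared case). Section 11.1 also lists false-discovery correction among its possible post hoc methods. What is missing is an explicit rule for the primary biomarkers.

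The discovery nature of the study excuses a rough effect size. It does not excuse two incompatible sample sizes.

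**Conclusion.** The inconsistency between 92 and 30-31 per arm is certain and rests on division alone: the plan means either 23 per arm, or 120-124 in total. The second conclusion is that the 90% power is not shown to apply to the four-arm design, because test, metric and number of groups are not stated. Its size is conditional. If .2 is f-squared in a one-way test at .01, four groups have 85.4% at 92, need 103 for 90%, and have 95-96% at 120-124. Other readings differ widely, and some repeated-measures readings reach 90%. A reader should not conclude that the 90% is wrong, only that it cannot be verified for this design. The third conclusion, that the alpha used for power is not the alpha stated for the primary tests, follows directly from 11.5 and 11.6.

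This should be corrected before the plan is relied on, because the stated sample size and its power justification do not agree with the design.

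**What to change.** 1. In 11.2 and 11.5, state one evaluable total with its matching four-arm number: either 92 (23 per arm) or about 120-124 (30-31 per arm). Say which enrolment figure (150 or 200) and which attrition rate it follows from.
2. Name the primary comparison, reconciling the memorandum's four-treatment objective with the secondary label that 11.6 gives Aim 2. Recompute its power for the design being run, stating the test, number of groups, effect metric, alpha, any assumed correlation and the software. If the result is below 90%, restate the power or report the detectable difference. If the primary comparison is between two arms, the table in step 5 gives the scale.
3. Make 11.6 match 11.5: apply the .01 threshold or a false-discovery-rate procedure to the primary biomarker tests, or recompute power at the alpha that will be used.
4. Settle the four-arm and three-arm wording in the Aim 2 sentence of 11.6, and bring 9.2 and Aims 2-4 into line with 9.4.
5. As a lesser clarification, say whether the ceiling of 200 counts consented or randomised participants.

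The cost is protocol wording and one recalculation. The ceiling of 200 and the equal allocation stay, with no added participants or procedures. The one possible loss is a less favourable stated power or detectable difference.
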